6.0 STRATIFICATION FACTORS

At registration patients will be randomized to receive Dexamethasone + either Low Dose or High Dose Carfilzomib. A dynamic allocation scheme will be used to balance treatment by the following two stratification factors:

1 - 3 prior therapies vs. 4-6 prior therapies.

Refractory to bortezomib vs. not refractory to bortezomib.

7.1 General Considerations

- a. Patients must have creatine kinase (CK), cardiac-specific troponin T (TnT) and/or troponin I (TnI) testing—both TnT and TnI preferred if available, creatine kinase-MB (CK-MB), brain natriuretic peptide (BNP) and/or proBNP performed on Cycle 1, Day 1. See [Section 9.0](#) for additional timepoints. In the event that Cycle 1, Day 1 laboratory tests are resulted and the patient no longer meets one or more of the eligibility criteria, treatment must be held. Laboratory tests and any associated supportive care must be repeated. If the repeat lab results fall within the eligibility criteria, treatment may be resumed. In the event that treatment must be held for \geq 28 days, the patient must be removed from the protocol.
- b. Patients on Arm 1 will receive dexamethasone/low-dose carfilzomib for up to 12 cycles or until progression that occurs after the start of Cycle 2, whichever comes first. If patient progresses after the start of Cycle 2 and prior to completion of 12 cycles, the patient will cross-over and be registered to Arm 3 where they may receive up to an additional 12 cycles of treatment.
- c. Results of Day 1 laboratory tests are not required prior to starting treatment for each cycle subsequent Cycle 1 (see Section 7.1a for instructions regarding D1, C1 results). If lab results are abnormal or indicative of adverse events, the treating physician should refer to Section 8.0 for dose modifications, and Response Assessments should be conducted at time of dose modification and as indicated in [Section 9.0](#). If dose modification is not indicated, the physician should otherwise continue treatment at physician discretion.
- d. Patients on Arm 2 will receive dexamethasone/high dose carfilzomib for up to 12 cycles, or until progression that occurs after the start of Cycle 2, whichever comes first. If a patient progresses after the start of Cycle 2, the patient will discontinue protocol treatment.

7.2 Pre-Medication

Prior to each dose in Cycle 1, 250-500 mL of intravenous normal saline will be given to reduce the risk of renal toxicity and of tumor lysis syndrome (TLS). An additional 250-500 mL of intravenous fluids as needed may be administered following carfilzomib administration, at the discretion of the treating physician. Intravenous hydration, as needed, may be given in subsequent cycles. Patients should be monitored during this period for fluid overload. Patients should not receive a total of more than 1 liter of intravenous hydration per administration. In the event of patient crossover to Arm 3, Cycle 1 intravenous hydration can be administered at physician discretion.

7.3 Registration Step 1 – Initial Registration (Arms 1 and 2)

a. Carfilzomib Dosing

For both treatment arms of the initial registration (Arms 1 and 2), carfilzomib will be administered at a dose of 20 mg/m^2 for Cycle 1. If tolerated in Cycle 1, the dose will be escalated to 27 mg/m^2 (Arm 1) or 56 mg/m^2 (Arm 2) beginning in Cycle 2 and continued in subsequent cycles. Note: Dose rounding is acceptable at the discretion of the treating physician; this must be documented on the **S1304** Treatment Form.

The carfilzomib dose will be calculated using the patient's actual body surface area at baseline. Patients with a body surface area greater than 2.2 m^2 should receive a dose based upon a body surface area of 2.2 m^2 . Dose adjustments do not need to be made for weight changes of less than or equal to 20%.

If a patient experiences any Grade 3 or 4 non-hematologic toxicity or Grade 4 hematologic toxicity in Cycle 1 that is considered to be related to study treatment, the second cycle of treatment will be given with carfilzomib at 20 mg/m^2 prior to escalation to the respective treatment dose for subsequent cycles. If a patient cannot undergo the dose escalation to the treatment dose despite being at 20 mg/m^2 for 2 cycles, they will be removed from protocol therapy.

b. Arm 1 – Dexamethasone + Low Dose Carfilzomib

Agent	Dose	Route	Day	Schedule*
Dexamethasone ^b	20 mg	IV	1, 2, 8, 9, 15, 16	up to 12 cycles
Carfilzomib ^a	20 mg/m^2	IV over 2-10 mins	1, 2, 8, 9, 15, 16	Cycle 1
Carfilzomib	27 mg/m^2	IV over 2-10 mins	1, 2, 8, 9, 15, 16	Cycles 2-12

* Note: 1 cycle = 28 days

^a See Section [7.3a](#) for Cycle 1 carfilzomib dosing and for dose capping based on BSA.

^b On all treatment days, dexamethasone will be administered 30 minutes prior to the carfilzomib infusion.

c. Arm 2 – Dexamethasone + High Dose Carfilzomib

Agent	Dose	Route	Day	Schedule*
Dexamethasone ^b	20 mg	IV	1, 2, 8, 9, 15, 16	up to 12 cycles
Carfilzomib ^a	20 mg/m^2	IV over 2-10 mins	1, 2, 8, 9, 15, 16	Cycle 1
Carfilzomib	56 mg/m^2	IV over 30 mins	1, 2, 8, 9, 15, 16	Cycles 2-12

* Note: 1 cycle = 28 days

^a See Section [7.3a](#) for Cycle 1 carfilzomib dosing and for dose capping based on BSA.

^b On all treatment days, dexamethasone will be administered 30 minutes prior to the carfilzomib infusion.

7.4 Registration Step – Crossover Registration (Arm 3)

Note that patients who cross over from Arm 1 to Arm 3 must be registered to Step 2 prior to initiation of cross-over treatment on Arm 3.

Agent	Dose	Route	Day	Schedule*
Dexamethasone ^b	20 mg	IV	1, 2, 8, 9, 15, 16	up to 12 cycles
Carfilzomib ^a	56 mg/m ²	IV over 30 mins	1, 2, 8, 9, 15, 16	Cycles 1-12

* Note: 1 cycle = 28 days

^a For Arm 3, Cycle 1 carfilzomib dosing is not reduced, but given at the full 56 mg/m² (see Section 7.3a for dose capping based on BSA).

^b On all treatment days, dexamethasone will be administered 30 minutes prior to the carfilzomib infusion.

7.5 Supportive Care and Concomitant Medication

a. Antiviral Prophylaxis

All patients should receive antiviral prophylaxis with acyclovir 400 mg orally two times daily (or an equivalent regimen as per institutional guidelines) while they are on study treatment. It is recommended that patients continue antiviral prophylaxis for at least 8 weeks after discontinuing treatment.

b. Pneumocystis Pneumonia (PCP) Prophylaxis

The probability of PCP should be considered based on previous treatments received and prophylaxis should be administered per local institutional guidelines at the discretion of the treating physician,

c. Concomitant Medication

Any systemic, anti-myeloma therapy or steroids other than those prescribed by the protocol are prohibited while on protocol therapy. Guidelines for selection and use of other concomitant medications should be derived from the carfilzomib and dexamethasone prescribing information. Other than study medications, administration of any therapeutic or diagnostic investigational agent (for any indication) is prohibited while on study.

d. G-CSF

G-CSF use is allowed in accordance with ASCO guidelines.

e. Bisphosphonates

Bisphosphonate use is allowed per local institutional guidelines at the discretion of the treating investigator.

f. Radiation Therapy

Radiation therapy is allowed per local institutional guidelines at the discretion of the treating investigator ONLY for localized disease symptom control.

g. Additional Monitoring

All patients will undergo EKG, ECHO and cardiac blood marker testing every 12 weeks while on study.

All patients that have evidence of extramedullary progression (EMP) will have a follow-up PET scan at the end of treatment or at the time of achieving VGPR or better, whichever occurs earlier (see Section [15.1](#)).

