 The usual natural history of MM involves periods of remission and episodes of relapse, evidenced by increased bone marrow plasmacytosis and end organ damage (renal failure, bone disease, anemia). In some cases, disease relapse is in the form of multiple solid extramedullary tumors, called plasmacytomas (EMP). (13) This is contrary to the general understanding of MM pathophysiology that the malignant clone depends heavily on the bone marrow microenvironment for its survival. (14) It is hypothesized that the malignant cells in EMP cases may undergo clonal terminal differentiation, so that they are capable of extravasation and homing to the extramedullary sites, and survival independent of the bone marrow cytokine milieu. (15) MM patients who have disease relapse with multiple EMPs follow a very aggressive course with extremely poor prognoses, and are resistant to most of the currently available treatment regimens. (1,16) So far this clinical entity has been recognized but efforts have not been directed to develop treatment regimens specifically for such MM patients. Furthermore, since the pathophysiology and clinical outcome of extramedullary and medullary relapses in MM are very distinct, exploration of differences in biological characteristics of these two entities is warranted. Recently, molecular profiling of MM cells has been characterized by gene expression profiling (GEP), especially by SWOG member institutions, and this

[figure not shown]

Figure 1: Risk group distribution and survival analyses, with Kaplan-meier estimates of EFS and OS between molecular risk groups in the test cohort.

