- 11 Pre-study (within 14 days prior to registration), then on Day 1 (\pm 3 days) of Cycles 2-12, then monthly until disease progression, at disease progression and at all follow up visits.
- 12 See Section [15.2](#).
- 13 Every 3 months after removal from protocol therapy for up to 3 years after initial registration, or more often if clinically indicated. For study purposes, response assessments (SPEP, immunoglobulins, 24 hour urine, serum/urine IFE, and CRP) are no longer required after progression or removal from trial due to toxicity.
- 14 See Section [7.0](#).
- 15 See Section [8.5](#) for treatment modification for cardiopulmonary events.
- 16 Unless otherwise noted, all required studies are to be performed on Day 1 of the treatment cycle.
- 17 At the time of progression, patients on Arm 1 may cross-over to Arm 3, providing they meet the additional criteria outlined in Section [5.2](#).
- 18 For patients with extramedullary progression (EMP), a follow-up PET scan at the end of treatment or at the time of VGPR, whichever occurs earlier, is required. See Sections [15.1](#) and Appendix [18.2](#) for requirements.
- 19 For patients that crossover to Arm 3, return to Cycle 1, Day 1, and follow the same study calendar. Assessments completed at time of progression on Arm 1, do not need to be repeated on Arm 3 (crossover) C1, D1, provided that ANC, platelets, SGOT, SGPT, serum creatinine, SPEP, and lambda light chain assessments are accomplished within 14 days prior to registration to Arm 3. All other assessments may have been accomplished anytime within 28 days prior to registration to Arm 3 (i.e. at time of progression on Arm 1). Note: Per eligibility criterion 5.2b, at least 14 days and no more than 28 days must have elapsed between the last day of treatment on Arm 1 and registration to Arm 3.

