11.6 Translational Medicine/Imaging Endpoints

GEP of the bone marrow plasma cells will be compared to that of an aspirate taken at the site of the EMP. Gene expression data will be log-transformed before any analysis. Exploratory analyses will be performed to examine the underlying distributions using boxplots, density plots, scatter plots, and so on. For differential expression analysis of the two sample types t-tests will be conducted upon tens of thousands of genes simultaneously. False discovery rate (FDR) will be used to control the average false positive proportions among selected genes. Genes will be ranked by their q-value and pathway analysis (www.ingenuity.com) will be conducted upon selected genes to ascertain biological plausibility and relevance to important molecular functionality.

Baseline PET images will be used to determine how many patients present with EMP. It is expected that 10-20% of patients (approximately 16-32 patients) will have EMP. For those patients, a second PET image will be taken when they achieve a VGPR or better, or at the end of their twelfth cycle of treatment, whichever is earlier. This second PET image will help determine response in those patients.

The main focus will be to determine the association of biochemical response with PET response for patients presenting with EMP at baseline. In this context a CR by PET will be defined by the disappearance of all focal lesions and the resolution of EMD. Univariate and multivariate logistic regression will be used to determine the impact of biochemical CR as defined in Section [10.1](#) on CR by PET. In the multivariate analysis adjustment for standard prognostic factors such as age, albumin, β -2 microglobulin, serum creatinine, CRP and LDH will be included.

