14.4 Data Submission Overview and Timepoints

- a. WITHIN 7 DAYS AFTER INITIAL REGISTRATION (STEP 1):

Submit the following:

S1304 Onstudy Form

FDG-PET and ECHO Images (see Appendix [18.2](#)). Retrospective ECHO image submission will also be requested for all patients.

PET Report

Specimens for TM and Banking (see Section [15.2](#))

- b. WITHIN 14 DAYS FOLLOWING EACH TREATMENT CYCLE:

Submit the following:

S1304 Treatment Form

Adverse Event Form

Follow-up Tumor Assessment Form for Multiple Myeloma

- c. AFTER COMPLETION OF CYCLES 3, 6, 9 AND 12 (including crossover to Arm 3):

Submit the following:

S1304 Cardiac Assessment Form

ECHO Images (see [Appendix 18.2](#)) (For crossover patients, ECHOs must be submitted every 3 cycles from the date of previous measurement.) Retrospective ECHO image submission will also be requested for all patients.

- d. WITHIN 7 DAYS OF ACHIEVING VGPR OR BETTER:

Submit the following:

FDG-PET and ECHO Images (see Appendix [18.2](#)). Retrospective ECHO image submission will also be requested for all patients.

PET Report

e. WITHIN 14 DAYS OF FIRST PROGRESSION/RELAPSE (ARMS 1 AND 2):

Submit the following:

Follow-up Tumor Assessment Form for Multiple Myeloma (if the patient was still on protocol treatment) or Follow-Up Form (if the patient was off protocol treatment) documenting date, site and method for determining progression/relapse.

Specimens for TM and Banking (see Section [15.2](#))

f. WITHIN 14 DAYS OF CROSSOVER REGISTRATION (STEP 2):

Submit the **S1304** Step 2 Eligibility Form

g. WITHIN 14 DAYS OF SECOND PROGRESSION/RELAPSE (ARM 3):

Submit the following:

Follow-up Tumor Assessment Form for Multiple Myeloma (if the patient was still on protocol treatment) or Follow-Up Form (if the patient was off protocol treatment) documenting date, site and method for determining progression/relapse.

Specimens for TM and Banking

h. WITHIN 14 DAYS OF DISCONTINUATION OF TREATMENT:

Submit the following:

Off Treatment Notice

S1304 Treatment Form

Adverse Event Form

(for patients with extramedullary disease) FDG-PET Image, unless submitted for VGPR (see Appendix [18.2](#))

ECHO Images (see [Appendix 18.2](#)). Retrospective ECHO image submission will also be requested for all patients.

S1304 Cardiac Assessment Form (if ECHO is performed)

i. EVERY 3 MONTHS AFTER OFF TREATMENT FOR UP TO 3 YEARS FROM INITIAL REGISTRATION:

Submit the Follow-up Form

j. WITHIN 4 WEEKS OF KNOWLEDGE OF DEATH:

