15.0 SPECIAL INSTRUCTIONS

15.1 FDG-PET Imaging (mandatory)

A standard FDG-PET scan will be obtained for all patients at the time of study entry and patients who have evidence of extramedullary progression (EMP) will have a second PET scan at the end of treatment or at the time of achieving a VGPR or better response, whichever occurs earlier. Note: The baseline PET scan may have been obtained as part of standard of care (prior to patient informed consent) provided that it was obtained within 28 days prior to registration. The follow up PET scan should occur at least 2 weeks after the last dose of study treatment received.

The funding of the second PET scan will be provided by the sponsor for the first 30 patients. Upon confirmation of receipt of the first 30 scans, a memorandum will be sent to investigators advising that no further patients should have PET scans submitted and that sites may remove the extra PET scan from their local consent forms.

Images will be submitted for central review via AG Mednet as outlined in Appendix [18.2](#) and will be reviewed by the PET Coordinator as outlined in Section [11.6](#).

Sites should obtain the AG Mednet Desktop Agent at the time of IRB approval (see Appendix [18.2](#)). Note that users must request access for this trial even if AG Mednet is being used for another SWOG trial.

FDG-PET studies will be acquired per standard clinical protocol. All studies will be performed as PET/CT, with inclusion of a dose-optimized CT study for attenuation correction and localization. The following scan parameters will be recorded at each site: administered activity (mCi), localization time (min), and injection site. Scans will include the whole body, from the vertex of the skull to the feet in order to include the entire skeleton.

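### The sections that order the second PET tie it to extramedullary progression, while the analysis needs it in patients with extramedullary disease at baseline, so some paired scans may be missed

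*Combined protocol and SAP*

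**What the plan says.** Three sections order the second scan, and each spells out EMP as progression:

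- Section 7.5g: "All patients that have evidence of extramedullary progression (EMP) will have a follow-up PET scan at the end of treatment", or at VGPR or better if that is earlier.
- Section 9.0, footnote 18: "For patients with extramedullary progression (EMP), a follow-up PET scan at the end of treatment or at the time of VGPR, whichever occurs earlier".
- Section 15.1: "patients who have evidence of extramedullary progression (EMP) will have a second PET scan at the end of treatment", again with VGPR or better as the earlier alternative.

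Two sections give the scientific purpose and use EMP differently:

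- Section 2.0 introduces it for plasmacytomas: "disease relapse is in the form of multiple solid extramedullary tumors, called plasmacytomas (EMP"). Under FDG-PET, the same section plans the follow-up scan for patients found to have EMPs before treatment starts.
- Section 11.6: "Baseline PET images will be used to determine how many patients present with EMP". The second image is then taken in those patients, and they are the population for the main PET analysis.

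The data schedule in Section 14.4 adds two more rules. Item d, headed "WITHIN 7 DAYS OF ACHIEVING VGPR OR BETTER", lists FDG-PET images and the PET report with no extramedullary restriction. Item h, at treatment discontinuation, has "for patients with extramedullary disease) FDG-PET Image, unless submitted for VGPR".

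Section 15.1 funds the second scan for the first 30 patients, after which sites are to be told to submit no more.

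**The concern.** One abbreviation carries two meanings, and the meaning used in the sections that order the scan is not the one used in the analysis. A patient with extramedullary disease at baseline that shrinks or stays stable is central to Section 11.6 but has no extramedullary progression. A site working only from 7.5g, footnote 18 or 15.1 could reasonably conclude that no second scan is due.

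The analysis relates biochemical CR to CR by PET in patients with baseline disease, and CR by PET requires that the extramedullary disease has resolved. If scans were obtained mainly after extramedullary progression, the paired set would contain few patients who could meet that definition, and the association would be poorly estimated in an unrepresentative group.

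Section 14.4d pulls the other way. Taken at face value it asks for images from responders who never had extramedullary disease, and those scans would count against a limited budget.

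**Working it through.** **Step 1. Who gets a second scan under each rule?** The table applies each section literally to five kinds of patient.

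| Patient | 7.5g, footnote 18, 15.1 | 14.4d | 14.4h | Wanted by 11.6 |
|---|---|---|---|---|
| Baseline extramedullary disease, reaches VGPR, no extramedullary progression | no | yes | not if sent at VGPR | yes |
| Baseline disease, never VGPR, no extramedullary progression | no | no | yes | yes |
| Baseline disease, never VGPR, extramedullary progression | yes | no | yes | yes |
| No baseline disease, reaches VGPR | no | yes | no | no |
| No baseline disease, new plasmacytoma on treatment, never VGPR | yes | no | arguably yes | no |

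The ordering sections omit the first two rows, which Section 11.6 wants, and include the last, which it does not. Sections 14.4d and 14.4h together reach all three rows that 11.6 wants, but 14.4d also takes in the fourth.

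**Step 2. Does the VGPR trigger make sense under the literal reading?** Section 10.1b counts new or definitely enlarging plasmacytomas as progression. VGPR requires all PR criteria, including at least a 50% reduction in any baseline plasmacytomas that are assessed. Extramedullary progression and VGPR therefore cannot hold at the same assessment. The VGPR timing could apply only in unusual sequences, such as an Arm 1 patient who progresses, crosses over to Arm 3 and then responds.

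**Step 3. How large is the intended group?** Section 11.6 gives 10-20%, which it translates to about 16-32 patients. Section 11.2 plans 140 patients, 126 of them eligible.

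- 0.10 x 140 = 14 and 0.20 x 140 = 28.
- 0.10 x 126 = 12.6 and 0.20 x 126 = 25.2.
- The stated 16-32 implies 16/0.10 = 32/0.20 = 160 patients, so it is not reproduced at 140 or 126. That is a separate matter; 14-28 is used here.

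The documents do not say what share of this group would have extramedullary progression, so the number missed cannot be computed.

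**Step 4. What would 14.4d add if used literally?** Let v be the proportion reaching VGPR or better and e the proportion with baseline extramedullary disease (10-20%). The documents give no v, so 10-40% is assumed, and v is assumed independent of e. Scans at VGPR = 140v. Those without baseline disease = 140(1 - e)v, and those with it = 140ev.

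| v (assumed) | Scans at VGPR | Without baseline disease | With baseline disease |
|---|---|---|---|
| 10% | 14 | 11.2-12.6 | 1.4-2.8 |
| 20% | 28 | 22.4-25.2 | 2.8-5.6 |
| 30% | 42 | 33.6-37.8 | 4.2-8.4 |
| 40% | 56 | 44.8-50.4 | 5.6-11.2 |

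Scans at VGPR alone would reach the cap of 30 at v = 30/140 = 21.4%. Restricted to baseline disease, 14-28 scans fit within it.

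**The case against.** The strongest reply is that a sensible site would read the ordering sections as meaning disease at entry. In Section 15.1 the EMP clause follows the study-entry scan in the same sentence and calls the next scan the second one. Section 15.1 refers to 11.6, and 7.5g refers to 15.1. Every patient enters relapsed or refractory, so extramedullary progression can mean extramedullary relapse already present at entry. The awkward VGPR trigger in Step 2 is itself evidence that the literal reading was not intended, and Section 2.0 states the intent plainly.

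This stands as an account of what was probably meant. It does not remove the conflict, because the three sections a site uses to order the scan all say progression. Section 14.4 governs submission: if no scan is ordered, there is nothing to submit.

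A reader might infer that sites will not scan the 11.6 group. The documents do not support that. Sections 14.4d and 14.4h between them list an image for every patient in the group, and 14.4d errs towards too many scans, not too few.

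A reader might also infer that 14.4d will exhaust the 30 funded scans on the wrong patients. That is not supported either. Section 14.4d is a submission schedule, nothing shows that it overrides the sections limiting the scan to EMP patients, and the counts in Step 4 rest on an assumed VGPR rate.

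The stakes are limited. PET is one of the other objectives (Section 1.3b), and Section 11.6 closes by describing these analyses as exploratory.

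**Conclusion.** The inconsistency is real and lies in the operative text. The supported conclusion is a risk: some of the 14-28 patients with baseline extramedullary disease may go without a second scan, mainly those who respond or stay stable, and the paired set would then lean towards progressors. The shortfall could run from none, if sites read EMP as disease at entry or work from Section 14.4, to most of the group if they follow the ordering sections literally and nothing else. The documents do not allow a point within that range to be chosen.

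The unneeded scans under 14.4d are also a possibility only: about 11-50 patients without baseline disease if VGPR rates were 10-40%, independent of extramedullary disease, and the item were followed literally. The consequence is confined to the exploratory PET analysis. The primary PFS comparison does not use the PET substudy population and is not affected.

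**What to change.** - In Section 7.5g, Section 9.0 footnote 18 and Section 15.1, replace *extramedullary progression (EMP)* with *extramedullary disease on the baseline PET*, in line with Sections 2.0 and 11.6.
- In Section 14.4d, add the same restriction to the PET images and PET report only, leaving the ECHO item as it is.
- In Section 14.4h, say that the extramedullary disease is that seen on the baseline PET.

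The cost is a few wording edits. No scans are added beyond those Section 11.6 already plans, and 14.4d may generate fewer. The study is closed to accrual, so for patients already off treatment the change cannot recover a missed scan. It would still guide sites with patients on treatment and fix which scans enter the analysis. A clarifying memorandum would do, as was used for the patient number in Section 11.8. The PET report should state how many patients had baseline extramedullary disease and how many of them had a second scan.
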